- The person in charge of the test will read grip strength in kilograms from the outside dial and record the result to the nearest 1 kg on the data entry form.
- The person in charge of the test will ask the participant to repeat measurement in the left hand.
- The participant will be asked to repeat two further measurements for each hand alternating sides to give three readings in total for each side.
- The best of the 3 grip strength measurements will be used in statistical analyses to encourage the subjects to get as high a score as possible.
- The person in charge will also record hand dominance, i.e. right, left or ambidextrous (people who can genuinely write with both hands).

For those participants that meet the previous inclusion criteria the following parameters will be explored:

1. Seated resting blood pressure.
2. Weight and height.

3. A finger stick blood sample (~1-2 drop equal to ~ 100ul) will be collected to confirm that subjects meet the inclusion criteria for fasting levels of blood glucose and cholesterol, plus a hematocrit to discard anemia.

Briefly, at Visit 0 (screening visit):

- Subjects will arrive fasted for at least 12 h prior to this visit (water ok).
- Informed consent will be obtained.
- ID number will be assigned.
- Hand grip strength test will be conduct.
- Seated resting blood pressure will be measured.
- Weight and height will be measured.
- A finger stick blood sample (~1-2 drop equal to ~ 100ul) to confirm that subjects meet the inclusion criteria (glucose, cholesterol and hematocrit).
- Diet history questionnaire (**Attachment C**) will be completed by the subjects to review medical history (including known positivity test for COVID-19), concomitant medications (including COVID-19 immunization dates), inclusion and exclusion criteria.
- This visit will take approximately 2 h to complete

9) Procedures Involved

Schedule of procedures

	Visit 0 Screening	Visit 1 Baseline	Visit 2 3-weeks visit	Visit 3 6-weeks final visit
Informed consent	X			
Inclusion / Exclusion criteria	X			
Review medical history	X			
Review concomitant medications	X		X	
Height, weight and blood pressure	X	X	X	X
Finger stick		X	X	X
Hand grip strength test	X	X	X	X
SPPB test		X	X	X

Blood draws for plasma determinations	X	X	X	X
Hematocrit	X	X	X	X
Study product randomization		X		
Study product intake			X	X
Dispense study product for home		X	X	
Return unused study product and empty packages			X	X
Dispense stool and urine collection kit		X	X	

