Return stool and urine collection kit			X	X
Adverse events assessment			X	X

After confirmation of the inclusion/exclusion criteria enrolled subjects will be asked to travel to Ragle Human Nutrition Center at University of California Davis for 3 study visits: a baseline visit (**visit 1**), and a 3-week intervention visit (**visit 2**) and a final 6-week visit (**visit 3**)

Visit 1 (baseline visit):

On this visit, baseline measurement will be done. Fasted participants (12 h) will provide blood samples and complete two tests:

Blood samples: from each participant 20 ml of blood will be extracted. The following parameters will be measured in plasma, (the same parameters will be measure in the following visits 2 and 3):

Blood parameter	Volume of blood needed	Visit 1	Visit 2	Visit 3
Irisin	1200 ul	X	X	X
Glucose	1000 ul	X	X	X
Insulin	1200 ul	X	X	X
GLP-1/ 2, GIP	2000 ul	X	X	X
Adiponectin, leptin and ghrelin	3000 ul	X	X	X
Blood urea nitrogen, creatinine	1000 ul	X	X	X
Total cholesterol, triglyceride, high-density lipoprotein (HDL), low-density lipoprotein	2000 ul	X	X	X
Aspartate transaminase, Alanine transaminase	2000 ul	X	X	X
IL-6, IL-15	2000 ul	X	X	X
25-hydroxyvitamin D	1000 ul	X	X	X
Hematocrit	500 ul	X	X	X

Total volume of blood per visit	~ 20 ml	20 ml	20 ml	20 ml
---------------------------------	---------	-------	-------	-------

After taking the blood samples a snack will be provided to the participants in order to complete the following tests.

1. Hand-grip strength: previously described in the screening point
2. Short Physical Performance Battery (SPPB): the SPPB score will be based on three tests, as follows: balance test, gait speed test, and chair stand test (see **Attachment E**). Of note, these tests have been used as a predictive tool for possible disability and can aid in the monitoring of function in older people.

Following, the subjects will randomize into the study supplement: a) Placebo powder (46 g placebo powder in 180 ml of water); or b) freeze-dried table grape powder (46 g grape powder in 180 ml of water). The supplement will be supplied to the participants to complete the following 3 weeks supplementation until the next visit. The investigator or designee will explain the details regarding the preparation and consumption of the supplement [a dosing protocol will be uploaded too (**Attachment F**)].

Also a 24-hs food and physical activity questionnaire will be performed

Briefly, at visit 1:

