- Subjects will arrive fasted for at least 12 h prior to this visit (water ok).
- A finger stick blood sample will be collected (to confirm fasting).
- Concomitant medications and accomplishment of inclusion and exclusion criteria will be reviewed.
- 24-hs food and physical activity questionnaire
- Seated resting blood will be measured.
- Weight will be measured.
- Venous blood samples will be collected for analytical determinations (20 ml).
- A hematocrit will be performed in order to discard anemia.
- Snack ingestion
- Hand grip strength and SPPB test will be completed.

- The supplement will be provided to the subjects for a 3 weeks supplementation period.
- Stool and urine collection kit and a standardized log and instructions (**Attachment G and H**) will be provided to subjects. The kits will be returned at visit 2.

Visit 2 (3-weeks visit):

Subjects will return to the Ragle Facility for the follow-up visit. This visit will take approximately 2 h to complete.

Briefly, at visit 2:

- Subjects will arrive fasted for at least 12 h prior to this visit (water ok).
- Subjects will provide fecal and urine samples collected with the collection kit.
- A finger stick blood sample will be collected (~1 drop).
- Concomitant medications and accomplishing of inclusion and exclusion criteria will be reviewed.
- 24-hs food and physical activity questionnaire
- Seated resting blood pressure will be measured.
- Weight will be measured.
- Subjects will take the assigned supplement.
- Venous blood samples will be collected (20 ml).
- A hematocrit will be performed in order to discard anemia.
- Snack will be provided to the participants.
- Hand grip strength and SPPB test will be completed.
- Enough supplement will be provided to the subjects for a 3 weeks supplementation period.
- Unused and empty packages of the study product will be return.
- Stool and urine collection kit will be provided to subjects. The kits will be returned at visit 3.

Visit 3 (final visit):

Subjects will return to the Ragle Facility for the final visit. This visit will also take approximately 2 h to complete.

Briefly, at visit 3:

- Subjects will arrive fasted for at least 12 h prior to this visit (water ok).
- Subjects will provide fecal and urine samples collected with the collection kit.
- A finger stick blood sample will be collected (~1 drop).
- Concomitant medications and accomplishing of inclusion and exclusion criteria will be reviewed.

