- 24-hs food and physical activity questionnaire
- Seated resting blood pressure will be measured.
- Weight will be measured.
- Subjects will take the assigned supplement.
- Venous blood samples will be collected (20 ml).
- A hematocrit will be performed in order to discard anemia.
- Snack will be provided to the participants.
- Hand grip strength and SPPB test will be completed.
- Unused and empty packages of the study product will be return.

10) Study Timelines

Duration of individual subject's participation will be ~6 weeks. The study will include: 1 visit (visit 0) for the screening process that will last approximately 2 h and 3 more visits (visits 1, 2 and 3) for intervention process that will last approximately 2 h each. Visit 0 will involve an in-person screening to obtain written informed consent and determine if subjects meet the inclusion/exclusion criteria. Visit 1, 2 and 3 (at 0, 3 weeks and at the end of the 6 weeks, respectively) will include blood sample collection and tests performance.

11) Study Endpoints

Primary endpoint:

Hand-grip strength media value of 16 kg or lower

Secondary endpoints:

Levels of Irisin as a marker of sarcopenia

Glucose, Insulin, GLP-1, GLP-2, GIP, Adiponectin, leptin and ghrelin, Blood urea nitrogen, creatinine, Aspartate transaminase, Alanine transaminase, Total cholesterol, triglyceride, high-density lipoprotein (HDL), low-density lipoprotein, IL-6, IL-15, 25-hydroxyvitamin D as markers of general metabolism state.

12) Data and/or Specimen Management and Confidentiality

Data management: The de-identified data will be analyzed for statistical significance with the help of the Biostatistics group at UC Davis, including univariate graphical, analytic summaries and bivariate relationships using box plots, scatter plots, and correlations. To compare participants in the two diet groups (Placebo control and freeze-dried table grape powder) a paired Student's t test (two-tailed) will be used. Data involving more than two repeated measures, such as grip strength tasks, or irisin levels, will be assessed by repeated measures (ANOVA). Differences will be considered significant at $P < 0.05$. Significant results will be also subjected to analysis of covariance (ANCOVA) to account for group differences at baseline and post hoc comparisons using the Bonferroni correction.

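### As listed, supplement intake comes directly before the venous draw at visits 2 and 3 but not at visit 1, so change from baseline in intake-sensitive markers mixes an acute response with the 3- or 6-week effect

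*Protocol*

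**What the plan says.** All references are to the protocol.

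- **Visit 1 (section 9).** "Fasted participants (12 h) will provide blood samples and complete two tests". A finger stick checks the fasting state. Food is held back: "After taking the blood samples a snack will be provided to the participants in order to complete the following tests". Randomization and dispensing come after the draw and the tests, so baseline blood is fasted and undosed.
- **Visits 2 and 3 (section 9).** Women again arrive fasted for 12 hours. The listed order is finger stick, reviews and questionnaire, blood pressure, weight, then "Subjects will take the assigned supplement", then "Venous blood samples will be collected (20 ml"), then hematocrit, snack, grip and SPPB. The two lists share this order.
- **Schedule of procedures (section 9).** The row "Study product intake" has two marks, read as visits 2 and 3, and none at baseline.
- **Assays (section 9).** One plasma panel serves all three visits: "the same parameters will be measure in the following visits 2 and 3".
- **Analysis (section 12).** Measures taken more than twice, with irisin as a named example, go to repeated-measures ANOVA. Significant results are followed by ANCOVA for baseline differences.

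The protocol states no interval between intake and draw, no pre-intake venous sample at visits 2 or 3, and no aim concerning the acute response to a dose.

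**The concern.** Section 2 asks what daily consumption does over the study period. To answer that from change in a plasma marker, the samples should differ in weeks of supplementation and not also in whether the woman has just taken 46 g of powder. As listed, they differ in both.

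The order also works against the protocol's own precautions. It asks for a 12-hour fast at every visit and withholds the snack until blood has been taken, yet at the follow-up visits the product would break that fast before the draw.

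The markers most exposed are glucose, insulin, GLP-1, GLP-2, GIP, ghrelin and triglycerides, all secondary endpoints in section 11. For these, within-arm change and the repeated-measures time effect would carry the acute response in full. The grape-placebo contrast would carry any difference in acute response between the two powders. Baseline ANCOVA cannot remove that difference, because it arises after baseline. Irisin, the outcome used for sizing in section 4, shares the sampling mismatch, but the protocol gives no acute effect for it.

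**Working it through.** **1. Sampling conditions side by side**

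| | Visit 1 | Visits 2 and 3 (as listed) |
|---|---|---|
| Arrival | fasted 12 h | fasted 12 h |
| Product before venous draw | none; not yet randomized | 46 g powder in 180 ml water |
| Interval from intake to draw | not applicable | not stated |
| Snack | after draw | after draw |
| Plasma panel | full | same panel |

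Follow-up samples affected: 14 women x 2 visits = 28.

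The blood table in section 9, leaving out hematocrit, lists 20 plasma markers: irisin; glucose; insulin; GLP-1, GLP-2, GIP; adiponectin, leptin, ghrelin; urea nitrogen, creatinine; total cholesterol, triglyceride, HDL, LDL; two transaminases; IL-6, IL-15; 25-hydroxyvitamin D. Seven are counted here as plainly intake-sensitive. That classification is a judgement; the protocol does not make it.

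**2. The plan's own figure**

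Section 4 gives 5 per group for 80% power at two-sided 0.05, with no effect size or SD, so it cannot be reproduced. Inverting it with the noncentral t gives a standardized effect of 1.68 (paired, 5 pairs) or 2.02 (two-sample, 5 per arm). The point made here does not depend on it.

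**3. What an acute shift would do if there were no lasting effect**

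Assumptions: 7 women per arm, no dropout, two-sided alpha 0.05, SD of the change score set to 1, lasting effect zero, acute shift *a* present at visits 2 and 3. The values *a* = 0.5 and 1 are illustrative.

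*Within-arm change, paired t.* df = 6, critical t = 2.447, noncentrality = a x sqrt(7).
- a = 0.5: noncentrality 1.323, rejection probability 0.201
- a = 1: noncentrality 2.646, rejection probability 0.600

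*Repeated-measures time effect, same shift in both arms.* With equal correlation between visits, a change SD of 1 means a within-woman error variance of 0.5. The visit means (0, a, a) have a sum of squares about their mean of (2/3)a². So λ = 14 x (2/3)a² / 0.5 = 18.67a², on 2 and 24 df, critical F = 3.403.
- a = 0.5: λ = 4.67, rejection probability 0.43 (simulation 0.423-0.428)
- a = 1: λ = 18.67, rejection probability 0.96 (simulation 0.960-0.961)

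*Grape-placebo contrast, same shift in both arms.* The shift cancels. Simulated rejection stays at 0.045-0.052 for every between-arm test.

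*Grape-placebo contrast, acute responses differing by a.* Two-sample t on change: df = 12, critical t = 2.179, noncentrality = a x sqrt(7/2).
- a = 0.5: noncentrality 0.935, rejection probability 0.139
- a = 1: noncentrality 1.871, rejection probability 0.406

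*The same differential shift, other analyses* (20,000 simulations each, within-woman correlation 0.5 and 0.7).
- Baseline ANCOVA: 0.147-0.158 at a = 0.5; 0.432-0.470 at a = 1. Adding a common 1 SD shift gives 0.422-0.471 at a = 1.
- Group-by-time: 0.132-0.139 at a = 0.5; 0.424-0.425 at a = 1.

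With 5 per arm the rates are lower: within-arm 0.141 and 0.401, between-arm change 0.108 and 0.286.

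**The case against.** **The lists may not be time sequences.** They are headed as brief summaries, and some entries are out of order. At visit 0 the text of section 8 puts the diet history questionnaire before grip testing, while the list puts it after. At visit 1 the text of section 9 mentions the food and activity questionnaire last, while the list has it before the draw. At visit 2 new product is listed before old packages come back. The fast and the delayed snack suggest that a fasted sample was meant, and Attachment F, which is not shown, may settle the timing. This stands as a reason to call the order a possible drafting slip. It does not clear the text. For the steps that matter (draw, snack, tests) the visit 1 list agrees with the visit 1 prose. Visits 2 and 3 have no prose sequence that would override their lists, and staff following the page would give the product first.

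**The placebo arm takes its powder too.** A shift common to both arms does cancel in the randomized contrast, so the 60% and 96% figures concern within-arm change and the time effect only. What remains between arms is any difference in acute response. Attachment J, which describes the placebo, is not shown, so its size cannot be judged.

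**A difference caused by that morning's dose is still caused by the product.** This is fair. The problem is which effect is being estimated, and the significant results above mislead only as evidence of a lasting effect.

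**The size is hypothetical.** The protocol gives no acute effect and no interval, and how far a marker such as triglyceride or GLP-2 would move depends on that interval. ANCOVA is planned only after a significant result, so its rates above are not those of the full procedure.

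**The reach is limited.** Grip strength, the primary endpoint in section 11, is untouched, and the seven markers are secondary. The finger stick at visits 2 and 3 is listed before intake, but it does not replace the venous panel.

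**Conclusion.** The concern holds as a statement about the written order. Visit 1 blood is fasted and undosed. The visit 2 and 3 lists place product intake directly before the draw, and nothing shown says otherwise. Followed as written, all 28 follow-up samples are taken under a different condition from baseline, and no later analysis can separate the acute response from the 3- or 6-week effect.

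The consequence depends on acute shifts that the protocol does not give. Over assumed shifts of 0.5 to 1 SD with no lasting effect and 7 per arm, a within-arm test rejects in 20% to 60% of trials and the time effect in about 43% to 96%. The grape-placebo change contrast stays at 5% if the shift is common to both arms, and rises to 14% to 41% if the arms differ by that amount. Whether irisin is affected cannot be told from the protocol. This should be fixed before the first follow-up visit; it does not threaten the grip strength endpoint.

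**What to change.** Reconcile the visit lists in section 9 so that venous blood is drawn in the same fasted, pre-intake state at visits 1, 2 and 3. Concretely, move the venous draw ahead of the in-clinic intake in the visit 2 and visit 3 lists, and check that Attachment F gives the same order.

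If a post-intake sample is wanted, list it as a separate sample, record the time since intake, and keep it out of the change-from-baseline endpoints.

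The main change swaps two bullets in each of two lists. It needs no extra blood, visits or staff, and it leaves the dose unchanged.

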levels compared to control and high fat diet groups (**Figure 2A-B**). Furthermore, supplementation with GPE led to the increase in irisin plasma level (**Figure 2C**)(11).

In order to understand the underlying mechanism involved in the GPE-related irisin increased levels, we next evaluated the effects of epicatechin, one of the main flavonoids present in GPE, in L6 myotubes challenged with palmitate, to mimic a condition of fatty acids oversupply. Protein levels of PGC- 1 α and FNDC5 were significantly higher in the EC and palmitate-treated cells, compared with palmitate-treated cells (**Figure 3A-B**). The same tendency was observed by immunocytochemical analysis of PGC-1 α , while no differences were observed in FNDC5 fluorescence intensity among treatments (**Figure 3D-E**). In addition, EC induced a 2-fold increase in irisin levels secreted to the medium compared with cells treated with only palmitate (**Figure 3C**). These data strongly indicate that phenolic compounds enhance irisin levels in vitro and in vivo.

These intriguing data allow us to hypothesize that phenolic compounds present in grapes might have a positive effect in human health, specially preventing sarcopenia in elderly humans, in part, by increasing irisin levels.

4) Enrollment Numbers

We chose the “changes in plasma irisin levels” as our primary outcome to determine the power calculations for sample size. Based on our preliminary data (11), 5 individuals per group are required to reach 80% power to detect differences in irisin levels between the groups, at a $\alpha=0.05$, using a two-sided paired T-test. We propose to enroll 7 individuals per group, instead of 5, in the event of a patient drop out of the study (for any unforeseen circumstances). In total we will have 14 subjects.

5) Inclusion and Exclusion Criteria

Inclusion Criteria: postmenopausal women aged 60 years or older with a hand-grip strength media value of 16 kg or lower, normal body mass index (BMI) with values between 18.4 and 24.9 kg/m², blood pressure below 130/80 mmHg, and plasma glucose and cholesterol concentrations below 100 and 200 mg/dl.

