After being pre-screened for eligibility by a phone interview, eligible potential participants will come to the Ragle Facility in a fasting (12 h) state for the in-person screening **visit 0**. In this visit the participants will sign an informed consent form. The subject will read the information carefully and will be given the opportunity to seek more information if needed. The investigator or designee will obtain written (signed and dated by the subject) informed consent from each potential participant after adequate explanation of the aims, methods and potential hazards of the study. The investigator or designee will also explain to the potential participant that his/her participation is voluntary, and he/she is free to withdraw from the study at any time. The investigator or designee will sign and date the consent form to confirm that the consent process was completed correctly. The subject will also be provided with the option of taking the consent form home to review prior to making his/her decision. The subject will be provided with a copy of his/her signed and dated consent form. Once consent has been obtained, the pre-screening visit will proceed. After the subject has signed the informed consent, an identification number (ID) will be assigned and entered the screening and enrollment log. A diet history questionnaire (**Attachment C**) will be complete by the participant.

After this we will confirm if they meet the following inclusion criteria:

1- Hand-grip strength media value of 16 kg or lower: Handgrip strength will be evaluated by using a digital dynamometer (Grip Strength Dynamometer T.K.K.5401; Takei Co., Tokyo, Japan). Following are the steps of the procedure [a detailed procedure will be added (**Attachment D**)]:

- The participant will be asked to seat comfortably in a standard chair with legs, back support and fixed arms.
- The participant will be asked to rest their forearms on the arms of the chair with their wrist just over the end of the arm of the chair wrist in a neutral position, thumb facing upwards.
- The person in charge of the test will demonstrate how to use the handgrip dynamometer.
- The participant will be asked to start with the right hand.
- The person in charge of the test will encourage the participant to squeeze as long and as tightly as possible or until the needle stops rising. Once the needle stops rising the participant can be instructed to stop squeezing.

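### The primary endpoint restates the entry criterion (grip 16 kg or lower), so it defines no outcome and does not match the planned analysis of grip

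*Protocol*

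**What the plan says.** - Protocol, Section 11 (Study Endpoints), gives the primary endpoint in full as "Hand-grip strength media value of 16 kg or lower". Irisin is listed there as secondary.
- Section 5 (Inclusion and Exclusion Criteria) admits "postmenopausal women aged 60 years or older with a hand-grip strength media value of 16 kg or lower".
- Section 8 (Screening procedures) places grip first under the line "After this we will confirm if they meet the following inclusion criteria", at visit 0. It also says: "The best of the 3 grip strength measurements will be used in statistical analyses".
- Section 9 (Procedures Involved) calls visit 1 the baseline visit, measures grip there before randomisation to grape powder or placebo, and repeats grip at visit 2 (3 weeks) and visit 3 (6 weeks).
- Section 12 (Data management) says: "Data involving more than two repeated measures, such as grip strength tasks, or irisin levels, will be assessed by repeated measures (ANOVA"). It adds ANCOVA for baseline differences where results are significant. It plans no analysis of a 16 kg threshold.
- Section 4 (Enrollment Numbers) calls the change in plasma irisin the primary outcome and sizes the trial on it: 5 per group, 7 enrolled, 14 in total.
- The lists for visits 2 and 3 in Section 9 include "Concomitant medications and accomplishing of inclusion and exclusion criteria will be reviewed", and visit 1 has a near-identical line. The schedule table marks the inclusion and exclusion check at visit 0 only.

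**The concern.** An endpoint has to be something that can differ between the arms after treatment. This one is the state on which the women were chosen. It gives no direction, no time point and no comparison, and read literally it describes the condition that the supplement is meant to improve. Section 12 then analyses a different variable, grip on its continuous scale, so a reader cannot tell which result decides Aim 1.

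This is not detail left to a statistical analysis plan. The protocol states a primary endpoint and states it wrongly, so a plan that analysed change in kg would contradict it. If someone did take the line at its word and counted women on either side of 16 kg, the cut would lie at the edge of the selected group, where ordinary measurement variation moves women across.

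**Working it through.** **1. The text side by side.** Entry rule (Section 5): grip 16 kg or lower. Primary endpoint (Section 11): grip 16 kg or lower. Share of eligible women who meet the endpoint at screening: 14/14 = 100%, by construction. Section 12 analyses grip as continuous over visits. The endpoint and the analysis are different variables.

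**2. The plan's own figure.** The 5 per group in Section 4 is for irisin, and no effect size or SD is stated, so it cannot be reproduced. Solving backwards at 80% power and two-sided 0.05, it implies a standardised effect of 1.68 (paired t, 5 pairs) or 2.02 (two-sample t, 5 per group). It says nothing about power for grip.

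**3. Crossing 16 kg with no true change.** Model: true grip T is normal with mean m; the screening reading is S = T + e0; a later reading is F = T + e1; the errors are independent. Women are selected if S ≤ 16, and the quantity of interest is P(F > 16 | S ≤ 16). The protocol gives none of the inputs, so all are assumptions, and two sets were simulated.

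Set A: between-woman SD 4.5 kg and session SD s. Reliability = 4.5²/(4.5² + s²), which is 20.25/21.25 = 0.95, 20.25/22.5 = 0.90 and 20.25/24.25 = 0.84.

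| m (kg) | s (kg) | Later reading > 16 kg | Mean rise from visit 0 |
|---|---|---|---|
| 18 | 1.0 | 13% | 0.24 kg |
| 20 | 1.5 | 25% | 0.66 kg |
| 22 | 2.0 | 39% | 1.39 kg |

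Set B: m 20 to 24 kg, total SD 4 to 5 kg, reliability r 0.80 to 0.95. The share runs from 17% (m 20, SD 5, r 0.95) to 57% (m 24, SD 4, r 0.80), and is 30% at m 22, SD 5, r 0.90. Mean rise = (1 − r) × (m − mean screening reading of those selected). For the 30% case this is 0.10 × (22 − 13.56) = 0.84 kg, which agrees with the simulation. Over the set the rise is 0.3 to 2.0 kg.

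In set B the same share already reads above 16 kg at visit 1, and the expected change from visit 1 to visit 3 is 0.

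**4. What a count could show with 7 per arm.** Fisher's exact test, two-sided:
- 0/7 v 5/7: 2 × 21/2002 = 0.021
- 1/7 v 6/7: 2 × 50/3432 = 0.029
- 2/7 v 7/7: 2 × 21/2002 = 0.021
- 3/7 v 7/7: 2 × 35/1001 = 0.070

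So three or more crossings on placebo rule out P < 0.05 in favour of grape powder. Expected chance crossings on placebo are 7 × 0.13 = 0.9 to 7 × 0.57 = 4.0. At a 30% chance rate, the probability of three or more is 1 − (0.082 + 0.247 + 0.318) = 0.35. Power of the count is about 7% for 20% v 50% and 28% for 20% v 70%.

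**5. Scoring.** The entry rule and endpoint use a media value (presumably the mean), but Section 8 analyses the best of three. For three normal readings the best exceeds their mean by about 0.85 reading SDs on average: 0.85 kg at SD 1.0, 1.27 kg at 1.5 and 1.69 kg at 2.0. The choice of score alone can put a woman on either side of 16 kg.

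**The case against.** The strongest reply is that the intent is clear and the analysis is sound: Section 12 treats grip as a continuous repeated measure with baseline adjustment, and no responder count is planned. That stands as far as it goes. Step 4 describes a literal reading of Section 11, not a planned analysis, and it would be wrong to say that counting is the only possible use of the line or that the trial cannot study grip at all. What remains is that the declared primary endpoint is not the variable analysed.

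Four stronger readings are tempting, and the protocol does not support them:
- *Regression to the mean biases the trial.* There is a randomised placebo arm, so the effect is equal in both arms in expectation. Grip is measured again at visit 1, before randomisation, and change from there is largely free of it.
- *Fasted screening against fed follow-up distorts the result.* At visit 1, "After taking the blood samples a snack will be provided to the participants in order to complete the following tests", and visits 2 and 3 also list a snack before grip. Only visit 0 differs, and it is not the baseline.
- *Women who improve past 16 kg will be removed.* Section 13 does not list grip among its reasons for removal, and at visits 2 and 3 the criteria review is listed before the grip test. No consequence is stated; the passages are simply not aligned.
- *The percentages are estimates for this trial.* They rest on assumed inputs, one selecting session and a single normal reading, and they ignore best-of-three scoring and recording to the nearest 1 kg. If the visit 1 criteria review also covers grip, selection would not rest on one session.

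**Conclusion.** The point holds as a defect in the stated endpoint. Section 11 repeats the Section 5 entry rule, is met by every eligible woman at screening, names no change, time point or contrast, and does not match Section 12. This rests on the text alone and needs no assumption.

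The size of chance crossing, roughly 13% to 57%, depends wholly on assumed means, spreads and reliabilities and applies only if the line is read as crossing 16 kg. On that reading the harm is inflated within-arm rates and lost information with 7 women per arm, not bias between arms. Two further conflicts bear on any repair: Section 4 names a different primary outcome, and grip has two scoring rules.

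**What to change.** 1. Section 11: replace the primary endpoint line with: Change in hand-grip strength (kg) from visit 1 (pre-randomisation baseline) to visit 3 (week 6), compared between grape powder and placebo. Keep 16 kg as an entry rule only.
2. Sections 5, 8 and 11: state one scoring rule for grip throughout, settling the media value against the best of three before screening starts, since the choice can affect who is eligible.
3. Section 4: reconcile with Section 11 so that only one primary is declared, and state that the power calculation refers to irisin. If grip stays primary, say that the sample size was not derived for it. If irisin is chosen instead, carry the new grip wording as a secondary endpoint.
4. Sections 9 and 13: reconcile the review of inclusion criteria at visits 1 to 3 with the schedule table (visit 0 only) and with the removal reasons, which do not mention grip.

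Cost: a wording amendment to these sections. Grip is already measured at visits 1, 2 and 3, so no new measurement, visit or participant is needed.
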